2.1.8 Rationale for study

The PD-1/PD-L1 pathway plays a major role in immune evasion and cytotoxic T-cell exhaustion in AML^{9,10,21}. PD-L1 expression in AML samples is increased at the time of disease progression or after exposure to IFN-gamma^{21,51}. Overexpression of PD-L1 is an independent negative prognostic factor in AML²¹. Hypomethylating agents may alter immune regulation⁵². Yang et al have recently demonstrated that hypomethylating therapy leads to up regulation of PD-L1, PD-1, and PD-L2 gene expression²⁰. Patients resistant to hypomethylating therapy had higher increments in gene expression suggesting that PD-1 up regulation may promote resistance to hypomethylating agents. Demethylation of the PD-L1 gene by chronic viral infection results in PD-L1 up-regulation and CTL exhaustion⁵³. Similarly, exposure to azacytidine up regulates PD-L1, PD-1 and PD-L2 by demethylation of the PD-L1 locus²⁰. These data suggest that blockage of PD-L1 by avelumab may improve response and abrogate resistance to hypomethylating agents. Furthermore, recent data shows that azacytidine increases NK-cell activating receptor ligands (NKG2DL) and enhanced ADCC when administered in combination with CD33-targeting antibody with preserved FCγIIIa domain (Vasu et al, Blood May 2016 and [name], Ravandi F et al, Blood May 2016). In addition to azacytidine's impact on T-cells costimulatory receptor and blast ligand expression we hope to promote ADCC by combining an epigenetic agent (azacytidine) with an agent that has preserved Fc receptor to engage NK cells (avelumab). Enhanced ADCC may be a second mechanism of antileukemic synergy when azacytidine and avelumab are administered in combination.

In this initial trial, we propose to explore these concept in patients with refractory/ relapsed AML with both clinical and focused correlative analysis. We propose to introduce PD-1

blockade early, when there are still leukemia cells that can prime the immune competent cells for eventual eradication. If the combination proves to be well tolerated and results in responses as expected, we would expand the use of this approach in the frontline setting for elderly AML and high-risk MDS (10-20% blast) patients who are not candidates for or refuse standard cytotoxic therapy either as an extension of this study or as a separate study.

3.0 STUDY DESIGN

- This will be a phase II, single-arm, open-label, non-randomized study with a safety lead-in phase IB.
- Patients will receive 5-azacytidine subcutaneously or intravenously daily for 7 days of each treatment cycle. For the lead-in phase IB portion, the length of the cycle will be at least 28 days to evaluate DLT. Subsequently, cycles will be repeated approximately every 28 days (+/-5 days), and therapy will be continued until clinically significant disease progression or documentation of unacceptable toxicity.
- Patients will receive therapy with avelumab IV infusion on Day 1 and day 14 (+/-3 days) of each 5-azacytidine cycle for first 4 cycles or until CR (whichever occurs earlier) followed by a maintenance regimen (one dose of avelumab on day 1 of each cycle of 5-azacytidine). Patients who have evidence of budding relapse or seem to have clinical benefit may continue or revert back to receiving avelumab on Day 1 and day 14 (+/-3 days) of each cycle of 5-azacytidine. Patients may receive avelumab more or less frequently during the maintenance regimen at the discretion of the treating physician only after discussion with the PI.
- The historical experience in relapsed/refractory AML patient population is that historical responses (CR/CRi/PR/Hi with >50% blast reduction) with single agent hypomethylator therapy (5-azacytidine or decitabine) or with hypomethylator combinations (azacytidine+revlimid, decitabine+myelotarg, azacytidine+vorinostat, decitabine+valproate) investigated at MDACC over the last 10 years are 10% ([name], Kantarjian H et al., European Hematology Association Conference, June 2016). In many instances (e.g., patients with relapsed/refractory AML beyond first salvage) no standard therapy is available. Thus, an overall response rate (CR/CRi/PR) of 30% will be considered significant

4.0 PATIENT SELECTION

4.1 Inclusion Criteria

- 4.1.1 Patients with AML who are refractory (up to salvage 2) or relapsed (up to 2nd relapse). For patients with prior MDS or chronic myelomonocytic leukemia (CMML) or MPN who transformed to AML, therapy received for MDS, CMML, or MPN is NOT considered as prior therapy for AML.
- 4.1.2 Prior therapy with hydroxyurea, chemotherapy, biological or targeted therapy (e.g.

FLT3 inhibitors, other kinase inhibitors), or hematopoietic growth factors is allowed.

- 4.1.3 Age ≥ 18 years
- 4.1.4 Eastern Cooperative Oncology Group (ECOG) Performance Status ≤ 2
- 4.1.5 Adequate organ function: total bilirubin ≤ 1.5 times upper limit of normal (x ULN) (≤ 3 x ULN if considered to be due to leukemic involvement or Gilbert's syndrome); aspartate aminotransferase or alanine aminotransferase ≤ 2.5 x ULN (≤ 5.0 x ULN if considered to be due to leukemic involvement)
- 4.1.6 Adequate renal function defined by an estimated creatinine clearance ≥ 30 mL/min according to the Cockcroft-Gault formula (or local institutional standard method)
- 4.1.7 Patients must provide written informed consent.
- 4.1.8 In the absence of rapidly progressing disease, the interval from prior treatment to time of initiation of 5-azacytidine and avelumab will be at least 14 days OR at least 5 half-lives for cytotoxic/noncytotoxic agents, whichever is longer. The toxicity from prior therapy should have resolved to Grade ≤ 1 , however alopecia and sensory neuropathy Grade ≤ 2 is acceptable. The half-life for the therapy in question will be based on published pharmacokinetic literature (abstracts, manuscripts, investigator brochure's, or drug-administration manuals) and will be documented in the protocol eligibility document. Since the effect of both avelumab and 5-azacytidine may be delayed, use of hydroxyurea for patients with rapidly proliferative disease is allowed before the start of study therapy and will not require a washout. Concurrent therapy for CNS prophylaxis or continuation of therapy for controlled CNS disease is permitted. Patients with CNS disease or leukemic brain metastasis must have been treated locally and be clinically stable for at least 2 weeks prior to enrollment and have no ongoing neurological symptoms that are related to the CNS disease (sequelae that are a consequence of the treatment of the CNS disease are acceptable).
- 4.1.9 Females must be surgically or biologically sterile or postmenopausal (amenorrheic for at least 12 months) or if of childbearing potential, must have a negative serum or urine pregnancy test within 72 hours before the start of the treatment.
- 4.1.10 Women of childbearing potential must agree to use an adequate method of contraception during the study and until 3 months after the last treatment. Males must be surgically or biologically sterile or agree to use an adequate method of contraception during the study until 3 months after the last treatment.

Adequate methods of contraception include:

- Total abstinence when this is in line with the preferred and usual lifestyle of the patient. Periodic abstinence (e.g., calendar, ovulation, symptothermal, post-ovulation methods) and withdrawal are not acceptable methods of contraception.
- Female sterilization (have had surgical bilateral oophorectomy with or without

hysterectomy) or tubal ligation at least six weeks before taking study treatment. In case of oophorectomy alone, only when the reproductive status of the woman has been confirmed by follow up hormone level assessment

- Male sterilization (at least 6 months prior to screening). For female patients on the study, the vasectomized male partner should be the sole partner for that patient
- Combination of any of the two following (a+b or a+c or b+c)
 - a. Use of oral, injected or implanted hormonal methods of contraception or other forms of hormonal contraception that have comparable efficacy (failure rate <1%), for example hormone vaginal ring or transdermal hormone contraception
 - b. Placement of an intrauterine device (IUD) or intrauterine system (IUS)
 - c. Barrier methods of contraception: Condom or Occlusive cap (diaphragm or cervical/vault caps) with spermicidal foam/gel/film/cream/ vaginal suppositoryIn case of use of oral contraception, women should have been stable on the same pill before taking study treatment.

Note: Oral contraceptives are allowed but should be used in conjunction with a barrier method of contraception due to unknown effect of drug-drug interaction. Women are considered post-menopausal and not of child bearing potential if they have had 12 months of natural (spontaneous) amenorrhea with an appropriate clinical profile (e.g. age appropriate, history of vasomotor symptoms) or have had surgical bilateral oophorectomy (with or without hysterectomy) or tubal ligation at least six weeks ago. In the case of oophorectomy alone, only when the reproductive status of the woman has been confirmed by follow up hormone level assessment is she considered not of child bearing potential.

4.2 Exclusion Criteria

- 4.2.1 Patients with a known allergy or hypersensitivity to avelumab, 5-azacytidine, or any of their components. Known severe hypersensitivity reactions to monoclonal antibodies (Grade ≥ 3 NCI-CTCAE v 4.03), any history of anaphylaxis, or uncontrolled asthma (that is, 3 or more features of partially controlled asthma).
- 4.2.2 Patients with a known history of severe interstitial lung disease or severe pneumonitis or active pneumonitis/pneumonia or pulmonary pathology that is not well controlled in the opinion of the treating physician and/or PI.
- 4.2.3 Patients who have previously been treated with avelumab (or another PD1/PDL1 inhibitor) in combination with 5-azacytidine will be excluded.
- 4.2.4 Persisting toxicity related to prior therapy of Grade >1 NCI-CTCAE v 4.03; however, alopecia and sensory neuropathy Grade ≤ 2 is acceptable
- 4.2.5 Active autoimmune disease that might deteriorate when receiving an immunostimulatory agent:
 - a. Subjects with diabetes type I, vitiligo, psoriasis, hypo- or hyperthyroid disease not requiring immunosuppressive treatment are eligible

- b. Subjects requiring hormone replacement with corticosteroids are eligible if the steroids are administered only for the purpose of hormonal replacement and at doses ≤ 10 mg or 10 mg equivalent prednisone per day
- c. Administration of steroids through a route known to result in a minimal systemic exposure (topical, intranasal, intro-ocular, or inhalation) are acceptable

- 4.2.6 Patients with organ allografts (such as renal transplant) are excluded
- 4.2.7 Patients who are <90 days post allogeneic stem cell transplant will be excluded. Patients beyond 90 days post-allogeneic stem cell transplant with uncontrolled active GVHD > grade 1 will be excluded. Patients who are on a stable dose of immunosuppressive therapy (tacrolimus, cyclosporine, or other) for > 2 weeks will be eligible but those with recent increase in the immunosuppressive medication dose within last 2 weeks to control GVHD will not be included. Note: Subjects may be using systemic corticosteroids or topical or inhaled corticosteroids post allogeneic stem cell transplant (inclusion based on post stem cell transplant activity and tolerability of checkpoint inhibitor by Matthew D, et al., ASH 2015 Annual Conference abstract # 860). Patients requiring ≥ 1 mg/kg prednisone for GVHD management at the time of screening will not be eligible until the prednisone can be weaned to <1 mg/kg. Such patients should be monitored for at least 14 days and if no flare of GVHD requiring re-escalation of steroids or additional interventions for the GVHD they will be eligible.
- 4.2.8 Patients with symptomatic CNS leukemia or patients with poorly controlled CNS leukemia.
- 4.2.9 Active and uncontrolled disease/(active uncontrolled infection, uncontrolled hypertension despite adequate medical therapy, active and uncontrolled congestive heart failure NYHA class III/IV, clinically significant and uncontrolled arrhythmia) as judged by the treating physician.
- 4.2.10 Patients with known Human Immunodeficiency Virus seropositivity will be excluded.
- 4.2.11 Known to be positive for hepatitis B by surface antigen expression. Known to have active hepatitis C infection (positive by polymerase chain reaction or on antiviral therapy for hepatitis C within the last 6 months)
- 4.2.12 Any other medical, psychological, or social condition that may interfere with study participation or compliance, or compromise patient safety in the opinion of the investigator
- 4.2.13 All other significant diseases (for example, inflammatory bowel disease, uncontrolled asthma), which, in the opinion of the Investigator, might impair the subject's tolerance of trial treatment
- 4.2.14 Patients unwilling or unable to comply with the protocol.

4.2.15 Pregnant or breastfeeding

4.2.16 Known alcohol or drug abuse within the last 1 year

4.2.17 Vaccination within 4 weeks of the first dose of avelumab and while on trial is prohibited except for administration of inactivated vaccines

4.2.18 Acute promyelocytic leukemia (APL).

4.2.19 Subject has a history of other malignancies prior to study entry, with the exception of:

- a. Adequately treated in situ carcinoma of the cervix uteri or carcinoma in situ of breast;
- b. Basal cell carcinoma of the skin or localized squamous cell carcinoma of the skin;
- c. Previous malignancy confirmed and surgically resected (or treated with other modalities) with curative intent or completed definitive therapy (chemotherapy, radiation, others) for the malignancy at least 1 year prior to the date of screening.

5 TREATMENT PLAN

5.1 General

All patients will be registered through CORe. We will first treat 6 patients at dose level -1.

5.2 Schedule

The Investigator is responsible for completing the cohort summary template and submitting to the IND office Medical Monitor for review and approval prior to advancing subjects to the next protocol specified cohort/dose level. A copy of the cohort summary should be placed in the Investigator's Regulatory Binder under "sponsor correspondence". This should be submitted after the first six patients.

5.2.1 Patients will be treated according to the following schedule:

- 5-azacytidine will be administered subcutaneously (SQ) or intravenously (IV) for 7 days of every cycle with daily schedule of 7 consecutive days (Days 1-7) or for days 5-2-2 which is 5 consecutive weekdays (Days 1-5) with rest on the 2 weekend days (Days 6 and 7) and then dosing the first two weekdays of the next week (Days 8 and 9) of each 28-day cycle as determined by treating physician. Alternative dosing schedules such as 4-2-3 which is 4 consecutive weekdays (Days 1-4) with rest on the 2 weekend days (Days 5 and 6) and then dosing the first three weekdays of the next week (Days 7, 8, and 9) of each 28-day cycle or other schedules allowing the 2 day weekend interruption may be applied as long as we make every attempt to give the 7 days of azacytidine as consecutively as possible. This must be clearly documented in the medical record as determined by treating physician after approval from the PI. Both SQ

and IV forms of administration are FDA approved and considered interchangeable. Patients may start receiving 5-azacytidine by one route and changed to the other, and also administration schedules from one schedule and changed to the other at any time as needed based on patient and/or physician preference.

- Avelumab will be administered as an approximately 60 minute (+/- 30 minutes) IV infusion on Day 1 and day 14 (+/-3 days) of each 5-azacytidine cycle for the first 4 cycles or until CR (whichever occurs earlier) followed by a maintenance regimen (one dose of avelumab on day 1 of each cycle of 5-azacytidine). Patients who have evidence of budding relapse or seem to have clinical benefit may continue or revert back to receiving avelumab on Day 1 and day 14 (+/-3 days) of each cycle of 5-azacytidine. Patients may receive avelumab more or less frequently during the maintenance regimen only after discussion with the PI. Avelumab will be administered every cycle with no interruptions unless there are adverse events as described in Section 5.3.
- 5-azacytidine at a dose of 75 mg/m² on days 1-7 or days 5-2-2 has been shown to be safe in combination with multiple agents including lenalidomide[60], bortezomib[60], and vorinostat[61, 62]. We have proposed the starting dose level -1 of 5-azacytidine 75 mg/m² x 7 days and avelumab 3.0 mg/kg on days 1 and 14 of each cycle. The lead-in phase is to ensure that the combination is well tolerated with no unexpected side effects and to identify the MTD of the combination. Avelumab infusion should begin right after the administration of 5-azacytidine on day 1, as described above, whenever possible. The dosing calculations should be based on the body weight. All doses should be rounded to the nearest milligram. There will be no dose reductions (only interruptions when indicated) allowed for avelumab on this trial.
- Avelumab administration: Subjects will receive avelumab by IV infusion following pretreatment with H1 blockers and acetaminophen on day 1 and 14 of each cycle. Premedication with an antihistamine and with paracetamol (acetaminophen) (for example, 25 50 mg diphenhydramine and 500-650 mg paracetamol [acetaminophen] IV or oral equivalent) approximately 30 to 60 minutes prior to each dose of avelumab is mandatory. This regimen may be modified based on local treatment standards and guidelines as appropriate provided it does not include systemic corticosteroids.

5.2.1.1 The starting dose will be dose level -1(Table 1).

Table 1. Dose levels of 5-azacytidine and avelumab during the lead-in phase (phase IB)

Dose level	5-azacytidine (mg/m²/d, Days 1-7)	Avelumab (mg/kg, day 1 and 14)
-3	25	3.0
-2	50	3.0
-1	75	3.0 (starting dose)

0	75	10.0 (target dose)
----------	-----------	---------------------------

- 5.2.1.4 We will first treat 6 patients at dose level -1 in the lead-in phase IB. If DLT occurs in $\geq 2/6$ patients, this dose level would exceed the MTD, and 6 patients will be treated at the next lower dose level (i.e. dose level -2). If DLT occurs in $< 2/6$ patients, this dose level would not exceed the MTD, and 6 patients will be treated at the next higher dose level (i.e. dose level 0). The dose de-escalation (Table 1) will continue in cohorts of 6 until we reach the maximum dose level at which $< 2/6$ patients experience a DLT in the first 28 days. The maximum dose level at which 0-1/6 patients experience a DLT in the first 28 days of treatment will be the MTD in this study and will be used to treat an additional 40 patients in the phase II portion of the study. If $\geq 2/6$ patients experience DLT at dose level -3, the study will be revised to consider additional lower dose levels (based on potential synergistic toxicity).
- 5.2.1.5 If DLT is observed in the first 28 days of treatment in 0 or 1/6 at dose level 0, then dose level 0 will be used for the phase II portion of the study.
- 5.2.1.6 Patients must receive a total of 7 doses of azacytidine and 2 doses of avelumab during the first 28 days on trial (i.e. during cycle 1) to be evaluated for DLT. Patients may have up to a total of 7 days interruption in the azacytidine dosing during the first 28 days and still be evaluable for DLT if the interruption is for complications or hospitalizations NOT related to the azacytidine or the avelumab. Patients who receive less than 7 doses of azacytidine and/or less than 2 doses of avelumab during the first 28 days on trial will NOT be evaluable for DLT. Patients not evaluable for DLT will be replaced. These patients may continue therapy on trial after discussion with the PI if they are having clinical benefit or if in the best interest of the patient and the reasons for continuation and potential benefit/risk profile for the patient must be clearly documented in the medical records.
- 5.2.1.7 Once MTD is defined, the RP2D will be selected based on efficacy and safety result from the phase I in discussion with the PI and the sponsor. The Investigator is responsible for completing the cohort summary template prior to advancing subjects to the phase II portion. Any patients still on study from the phase I portion at a dose lower than RP2D can be dose escalated up to RP2D. However, the dose for any patient may never exceed the RP2D.
- 5.2.1.8 Once MTD is defined, the RP2D will be selected based on efficacy and safety result from the phase I in discussion with the PI and the sponsor. The Investigator is responsible for completing the cohort summary template prior to advancing subjects to the phase II portion. Any patients still on study from the phase I portion at a dose lower than RP2D can be dose escalated up to RP2D. However, the dose for any patient may never exceed the RP2D.

- 5.2.2 One cycle of therapy is defined as 28 days. Patients will receive one cycle of therapy every 28 days (+/- 5 days).
- 5.2.2.1 In the phase II portion of the study (once the MTD dose has been defined) cycles may be started early (but not earlier than day 23) for patients with active disease if judged in the best interest of the patient.
For the lead-in cohort, DLT defining period is 28 days. As such, cycle 2 should not be started before 28 days for the patients being treated on the lead-in cohort.
- 5.2.2.2 Subsequent cycles may be delayed for recovery of toxicity or other medical conditions (e.g. infections). Delays in start of subsequent cycles greater than 8 weeks will be acceptable only for patients who are deriving clinical benefit and after discussion with the principal investigator of potential risk/benefit ratio and clear documentation in the medical record of the reason for continuation and perceived benefit to the patient from continuation of this therapy.
- 5.2.2.3 In instances where one drug has to be discontinued transiently because of safety, the administration of the other drug may continue as scheduled.
- 5.2.2.4 Azacitidine and avelumab will be held during phase II of the study, for grade 4 neutropenia or grade 4 thrombocytopenia lasting ≥ 42 days from the start of each cycle, in the absence of evidence of active AML. If prolonged grade 4 neutropenia (more than 42 days) WITH evidence of a hypocellular marrow (marrow cellularity less than 5% without evidence of leukemia) is observed, 5-azacytidine and avelumab will be discontinued. Delays in start of subsequent cycles greater than 42 days will be acceptable only for patients who are deriving clinical benefit and after discussion with the principal investigator of potential risk/benefit ratio.
If the peripheral counts do not recover ($ANC < 0.5 \times 10^9/L$ and/or platelets $< 25 \times 10^9/L$) but there is evidence of residual leukemia by morphology or flow-cytometry in the bone marrow, subsequent cycles can be administered at the discretion of the treating physician not earlier than 23 days after the prior cycle in the phase II portion of the study. For the lead-in cohort, DLT defining period is 28 days. As such, cycle 2 should not be started before 28 days for the patients being treated on the lead-in cohort.
- 5.2.2.5 For patients who discontinue therapy, the reason for treatment discontinuation will be captured.

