 - Grade 3 lymphopenia or leukopenia does not require dose delay.
 - However, patients with ALT or AST > 5 x ULN or total bilirubin greater > 3 x ULN or creatinine > 3 x ULN should have avelumab treatment interrupted.
- Any AE, laboratory abnormality, or intercurrent illness, which in the judgment of the investigator, warrants delaying the dose of study medication.
- Avelumab dose reductions are not permitted in this study (only dose delays when indicated).

Subjects may resume treatment with study drug when the drug-related AE(s) resolve to Grade ≤ 1 or baseline value, with the following exceptions:

- Subjects may resume treatment in the presence of Grade 2 fatigue
- Subjects who have not experienced a Grade 3 drug-related skin AE may resume treatment in the presence of Grade 2 skin toxicity
- Drug-related pulmonary toxicity, diarrhea, or colitis, must have resolved to baseline or at least \leq grade 1 before treatment is resumed
- Drug-related endocrinopathies adequately controlled may resume treatment

If the criteria to resume treatment are met, the subject should restart treatment at the next scheduled time point per protocol. However, if the treatment is delayed past the next scheduled time point per protocol, the next scheduled time point will be delayed until dosing resumes. Patients who receive combination therapy in whom continuation of 5-azacytidine is considered to be inadequate, or inappropriate (e.g., because of pancytopenia) can discontinue 5-azacytidine and continue with avelumab only.

If treatment is delayed > 8 weeks, the subject must be permanently discontinued from study therapy, except as specified in discontinuation section.

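### The lead-in DLT evaluability rule sets no latest day for the second avelumab dose and no minimum follow-up after it, so a late dose can leave a patient counted as a full no-DLT after 0 to 10 days

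*Combined protocol and SAP*

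**What the plan says.** **Evaluability (5.2.1.6).** "Patients must receive a total of 7 doses of azacytidine and 2 doses of avelumab during the first 28 days on trial" is the condition for being assessed for DLT. "Patients who receive less than 7 doses of azacytidine and/or less than 2 doses of avelumab during the first 28 days on trial" describes those who are not evaluable and are replaced. The only limit on interruptions concerns the other drug: "Patients may have up to a total of 7 days interruption in the azacytidine dosing during the first 28 days", and only for reasons unrelated to either agent. Avelumab has no counterpart.

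**Schedule (5.2.1).** Avelumab is given by "IV infusion on Day 1 and day 14 (+/-3 days) of each 5-azacytidine cycle for the first 4 cycles" (or until CR, if earlier), "with no interruptions unless there are adverse events as described in Section 5.3".

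**Delay (5.3.3).** Avelumab is held for drug-related non-skin events of Grade 2 or higher, with exceptions such as fatigue, and for any event or intercurrent illness that the investigator judges to warrant it. Two sentences govern restarting. The first restarts the patient at the next scheduled time point. The second says that "if the treatment is delayed past the next scheduled time point per protocol, the next scheduled time point will be delayed until dosing resumes".

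**DLT definition and window.** The definition (after 5.2.1.3) is mainly Grade 3 or 4 non-hematologic events in the first cycle. A Grade 2 event or a delayed dose is not on the list. Section 5.2.2.1 states: "For the lead-in cohort, DLT defining period is 28 days". Sections 5.2.1.4, 5.2.1.5 and 11.2 apply the 0-1/6 rule to the first 28 days.

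**The concern.** The evaluability rule should ensure that each of the six patients behind a level decision has been exposed to both avelumab doses and watched long enough for toxicity to appear. As written it secures the exposure but not the watching. A patient dosed on day 25 has 3 days of observation after dose 2 and carries the same weight as one dosed on day 14 with 14 days.

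Missed DLTs can only lower the count, so the error has a known direction. Cohorts are six patients, a single DLT can reverse the decision, and the chosen level then treats up to 40 more patients. Avelumab is also the drug that rises between dose level -1 (3.0 mg/kg) and dose level 0 (10.0 mg/kg).

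**Working it through.** **1. The plan's own lead-in figure.** Cohorts are six per level. Level -1 then 0 gives 12; level -1 then -2 gives 12; levels -1, -2 and -3 give 18. Adding 40 gives 52 to 58, which matches 11.1. No operating characteristics are stated for the lead-in.

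**2. Follow-up after dose 2.** Days observed = 28 - day of dose 2.

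| Day of dose 2 | 11 | 14 | 17 | 18 | 21 | 24 | 28 |
|---|---|---|---|---|---|---|---|
| Days observed | 17 | 14 | 11 | 10 | 7 | 4 | 0 |

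On schedule the range is 11 to 17 days. For days 18 to 28 it is 0 to 10. One DLT criterion requires Grade 3 AST/ALT or bilirubin to last at least 7 days. A rise that starts after a dose later than about day 21 cannot meet that criterion by day 28.

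**3. Can a late dose 2 occur in cycle 1?** Under the second restart sentence of 5.3.3, yes: the day 14 dose moves until dosing resumes. Under the first, a missed day 14 dose waits for cycle 2 day 1. By 5.2.2.1 that is not before 28 days in the lead-in, so the patient would have one dose in cycle 1 and be replaced. The text does not say which applies to a held lead-in dose.

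**4. Illustration on assumed inputs.** Let p be the true DLT risk under full observation, s the share of it falling after dose 2, and k the number of late patients among six. Assume no observation after a late dose. A late patient's counted risk is q = p(1 - s), and the level passes with 0 or 1 DLT. The documents give neither s nor k, so s runs over 25%, 50% and 75%.

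With p = 1/3 and k = 0: (2/3)^6 + 6(1/3)(2/3)^5 = 0.351.

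With k = 1, the five other patients have P(0) = (2/3)^5 = 0.1317 and P(1) = 5(1/3)(2/3)^4 = 0.3292, so P(pass) = 0.1317 + 0.3292(1 - q).

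With k = 2, the four others have P(0) = 0.1975 and P(1) = 0.3951, so P(pass) = 0.1975[(1 - q)^2 + 2q(1 - q)] + 0.3951(1 - q)^2.

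| s | q | k = 1 | k = 2 |
|---|---|---|---|
| 25% | 0.250 | 0.379 | 0.407 |
| 50% | 0.167 | 0.406 | 0.466 |
| 75% | 0.083 | 0.434 | 0.528 |

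Splitting the risk on the hazard scale instead, q = 1 - (1 - p)^(1 - s), gives q = 0.262, 0.184 and 0.096. P(pass) is then 0.375, 0.400 and 0.429 with one late patient, and 0.399, 0.454 and 0.518 with two. Over both splits the ranges are 0.37-0.43 and 0.40-0.53.

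**The case against.** **The next-time-point sentence may already exclude these patients.** If a held day 14 dose is skipped to cycle 2, the patient is replaced and no truncated observation enters the count. This stands as one of two readings. A reader might infer that every patient with a delayed second dose is scored as a no-DLT; the documents do not support that.

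**The route is narrow.** Most Grade 3 and nearly all Grade 4 events end avelumab under 5.3.4. Grade 2 fatigue and most Grade 2 laboratory changes need no delay. Where Table 3 calls for steroids in Grade 2 events, the taper lasts at least a month, which generally carries resumption past day 28. What remains is mainly a Grade 2 event that settles without a taper, or intercurrent illness. This stands and limits how often the gap can arise. It also means one cannot say that the truncated patients are mainly those with prior drug toxicity: 5.3.3 allows holds for other illness, and 5.6 calls infections common in AML.

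**The window is not always 28 days.** The definition refers to the first cycle, Section 3.0 makes the lead-in cycle at least 28 days, and one criterion is neutropenia lasting 42 days or more. This shows that the wording is inconsistent. It does not close the gap, because every decision rule counts to day 28.

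**The probabilities are not properties of the plan.** Correct. They also fix in advance which patients are late, although a patient with a DLT after dose 1 would ordinarily not receive a late dose 2.

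**Other safeguards exist.** Under 11.2 a toxicity summary goes to the Medical Monitor every three evaluable patients. The RP2D choice uses safety beyond the DLT count, and phase II has a toxicity stopping rule. These reduce the consequence but do not correct the 0-1/6 count.

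**Conclusion.** The gap is real and follows from the text, on the reading of 5.3.3 that lets a held dose be given later in cycle 1. Such a patient can be counted as a full no-DLT with 0 to 10 days of observation after the second dose, against 11 to 17 on schedule, and the error runs toward passing a level that is too toxic. How often this would happen, and how far it would shift the decision, cannot be derived from the documents, which give neither a delay frequency nor the timing of DLTs. The illustrated increases, from 0.35 to 0.37-0.43 or 0.40-0.53, rest on an assumed true risk of 1/3, an assumed 25% to 75% share after dose 2, and no observation after the late dose. They show that one or two such patients could matter in a cohort of six. They do not estimate the trial's actual error rate. The change is worth making because it is cheap and the direction of the error is clear.

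**What to change.** In 5.2.1.6, state that if the second avelumab dose is given after day 17, DLTs for that patient are counted to the later of day 28 or 11 days after that dose, including events after cycle 2 has started. State also that the level decision waits for this observation. Eleven days is the shortest follow-up the plan's own window gives (28 - 17).

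Align the 28-day and first-cycle wording in the DLT definition, 5.2.1.4, 5.2.1.5, 5.2.2.1, 5.2.2.4, 11.1 and 11.2. Reconcile 5.2.1.6 with the two restart sentences in 5.3.3, so that it is clear whether a held lead-in dose leads to late dosing or to replacement. None of this changes when or whether drug is given; it changes only how long DLTs are counted.

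Cost: a short amendment touching several sections. A level decision comes up to 11 days later (dose on day 28, observed to day 39), and only when a second dose was late. Because cycle 2 may start from day 28, part of the extension may overlap cycle 2 exposure, so an event then may be harder to attribute to cycle 1.
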